### **Statistical Analysis Plan**

The sample size was calculated using the GPower v. 3.1 program [64] based on the following outcomes: MNSI DPN symptoms (primary) and ankle sagittal ROM during gait (secondary). These two outcomes were chosen because they reflect important functional gains for DPN patients. Thus, two sample size calculations were performed, and we selected the one that resulted in the largest number of participants. The effect sizes used for both calculations were based on a study that evaluated the effect of 12 weeks of supervised foot exercise in DM patients [34]. In that study, the improvement in the MNSI symptoms had a medium effect size

(0.52), as did gains in the ankle sagittal ROM during gait (0.46). We chose to use half of the effect size obtained in [34] because the nature of our intervention is home based, whereas Sartor's was face-to-face, which is assumed to be more effective.

The input factors for sample size calculation were a statistical design of F-test with interaction between and within factors with two repeated measures and two study groups, statistical power of 0.80, alpha of 0.05, and effect sizes of 0.26 (MNSI symptoms) and 0.23 (ankle ROM). The resulting sample sizes were 32 and 40 individuals for MNSI and ROM outcomes, respectively. Therefore, we defined our sample size as 40. Assuming a 20% dropout rate during the study, a sample size of 48 patients is needed.

Inferential statistical analyses will be conducted using intention-to-treat and per protocol analyses. The missing data will be treated by imputation methods depending on the type: missing completely at random, missing at random, or not at random [65]. The per-protocol analysis will include only those patients who complete follow-up in the allocated intervention group. Confirmation of normality (Kolmogorov–Smirnov test), homoscedasticity (Levene test), and imputation of the means for the missing data of variables with normal distribution will be conducted. After that, mixed general linear models of analysis of variance for repeated measures will be used to detect treatment–time interactions, followed by Newman–Keuls post hoc test to obtain group effect (intervention and control), time effect (between T0, T8, and T16), and group–time interaction. Significant differences will be considered at  $\alpha = 5\%$ , but for the description of the effect of the intervention, the effect size (Cohen coefficient) and difference between the means will be calculated with their respective 95% confidence intervals.

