## **Participants and recruitment**

This study is currently recruiting patients (study start date: May 1, 2019) with a medical diagnosis of DM and DPN from the Department of Endocrinology of the Hospital das Clínicas of the School of Medicine of the University of São Paulo. Forty-eight participants with DPN will be recruited. The potential subjects will be interviewed by telephone and, once selected, assessed in the laboratory to confirm all eligibility criteria. This first laboratory assessment will represent the baseline condition (blind assessment).

The inclusion criteria are adults up to 65 years of age of either sex diagnosed with DM type 1 or 2 with at least mild DPN confirmed by a fuzzy logic-based system [13], who are able to walk independently for at least 10 m, and who do not have more than one amputated toe (that is not the hallux). The exclusion criteria are the presence of an ulcer not healed for at least 6 months and/or active ulcer; a history of surgical procedure to the knee, ankle, or hip or indication of surgery throughout the intervention period; arthroplasty and/or orthosis of lower limbs or indication of lower limb arthroplasty throughout the intervention period; diagnosis of other

neurological disease outside of DM consequences; dementia or inability to give consistent information; receiving any physiotherapy or offloading devices throughout the intervention period; having major vascular complications and/or severe retinopathy; or having a score of 12–21 (probable depression) on the Hospital Anxiety and Depression Scale (HADS).

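### 48 patients allow for 16.7% dropout, not the stated 20%: at 20%, about 38 complete, 2 short of the 40 set by ankle ROM (secondary), while the 32 for MNSI (primary) is still met

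*Combined protocol and SAP*

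**What the plan says.** The Statistical Analysis Plan sizes the trial on two outcomes, MNSI symptoms (primary) and sagittal ankle ROM during gait (secondary), and takes the larger result. The inputs are a "statistical design of F-test with interaction between and within factors with two repeated measures and two study groups", with "statistical power of 0.80, alpha of 0.05", and effect sizes of 0.26 for MNSI and 0.23 for ROM. It reports: "The resulting sample sizes were 32 and 40 individuals for MNSI and ROM outcomes, respectively". It continues: "Therefore, we defined our sample size as 40". The dropout step follows: "Assuming a 20% dropout rate during the study, a sample size of 48 patients is needed". No formula is given for that step, and no correlation between repeated measures is stated.

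The Participants and recruitment section carries the number forward: "Forty-eight participants with DPN will be recruited". On analysis sets, the plan names both intention-to-treat with imputation and per protocol. Of the latter it says: "The per-protocol analysis will include only those patients who complete follow-up in the allocated intervention group".

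**The concern.** A dropout rate applies to the patients enrolled. If 20% of them are lost, 80% remain, so the number required must be divided by 0.80. Adding 20% of the required number to itself gives a smaller figure, and 48 is exactly that figure. If so, the plan claims protection against a level of attrition that its recruitment target does not provide.

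At stake is whether the trial would still hold the 40 patients it defined as its sample size if its own dropout assumption came true, and whether either sizing outcome would then fall below the 80% power target. The per-protocol set is the most directly exposed, because it is limited to patients who complete follow-up.

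**Working it through.** **Inputs from the plan.** Required N of 32 (MNSI) and 40 (ROM); chosen N of 40; dropout 20%; recruitment target 48; two groups, two measures, power 0.80, alpha 0.05; effect sizes 0.26 and 0.23.

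**Assumptions not in the plan.** The effect sizes are entered as Cohen's f, and the correlation between measures is ρ = 0.5. Both are inferred because they reproduce the plan's figures. They are needed only for the power results (steps 1, 4 and 5), not for the dropout arithmetic (steps 2 and 3).

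**1. Reproduce the sizes before dropout.** Noncentral F test for the group-by-time interaction, with m = 2 measures, λ = f² × N × m/(1 − ρ), and df = 1 and N − 2.

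- MNSI, N = 32: λ = 0.26² × 32 × 2/0.5 = 8.65; power 81.2%.
- ROM, N = 40: λ = 0.23² × 40 × 2/0.5 = 8.46; power 80.9%.

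With equal groups, these are the smallest sizes that reach 80%, so 32 and 40 are both reproduced. Correlations further away do not fit: ρ = 0.4 gives 38 and 48, and ρ = 0.6 gives 26 and 32. Only ρ from about 0.488 to 0.514 returns both stated sizes.

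**2. The dropout step.**

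- Adding 20% of the required number: 40 × 1.20 = 48, the plan's figure exactly.
- Keeping 40 after a 20% loss: 40/(1 − 0.20) = 50.

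**3. What 48 delivers.**

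- Expected completers at 20% dropout: 48 × 0.80 = 38.4. That is 1.6 below 40, or 2 in whole patients.
- Losses tolerated before falling below 40: 48 − 40 = 8, and 8/48 = 16.7%.
- Losses tolerated before falling below the 32 for MNSI: 48 − 32 = 16, and 16/48 = 33.3%.
- Enrolment that MNSI alone would need at 20% dropout: 32/0.80 = 40.
- If each patient drops out independently with probability 0.20, the chance of at least 40 completers is 36% with 48 enrolled and 58% with 50. The chance of at least 32 with 48 enrolled is 99%.

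**4. Power in the two-measure planning model (ρ = 0.5).**

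| Completers | ROM (f = 0.23) | MNSI (f = 0.26) |
|---|---|---|
| 32 | 71.2% | 81.2% |
| 38 | 78.8% | 87.7% |
| 39 | 79.9% | 88.5% |
| 40 | 80.9% | 89.3% |

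Over the correlations that reproduce both stated sizes (about 0.488 to 0.514), power at 38 runs from 77.8% to 79.9% for ROM and from 86.9% to 88.6% for MNSI.

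**5. Three time points.** The planned analysis uses T0, T8 and T16. With m = 3, ρ = 0.5 and sphericity, the same method gives 87.1% for ROM at 38 completers.

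**The case against.** The strongest reply is that nothing of consequence changes. The expected shortfall is 1.6 patients, the cost is about 2 points of power on a secondary outcome, and the primary outcome is well covered. The analysis will use three time points, for which the same method gives about 87% for ROM at 38 completers, above the 80% target. Intention-to-treat with imputation would nominally keep all 48. It can also be said that power figures resting on an unstated correlation do not belong in the plan, and that enrolling 50 would be the direct correction if 20% is the real expectation.

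Much of this stands as a limit on size:

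- The effect is minor, and MNSI is not left underpowered.
- The three-measure result softens the consequence, although it assumes that the effect size, correlation and sphericity carry over, which the documents do not establish.
- The plan shows no formula, so adding 20% to 40 is an inference from an exact match, not a documented step.
- The power figures do depend on the inferred correlation, so they should be labelled as such and confirmed.

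None of it makes the dropout statement true. Imputed values do not restore lost information, the per-protocol set counts completers only, and the plan itself chose 40 as its benchmark and inflated it for dropout. Enrolling 50 would also repair the statement, but it means more patients in a trial already recruiting, for a gain confined to a secondary outcome.

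**Conclusion.** The concern holds. On the plan's own figures, 48 enrolled does not keep 40 patients through a 20% dropout. It does so only up to 16.7%, and at 20% about 38 remain. This needs no assumption beyond reading the dropout rate as a share of those enrolled.

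The consequence is small and confined to the ankle ROM calculation, where power in the two-measure model slips from 80.9% to 78.8% (77.8% to 79.9% over the compatible correlations). MNSI stays well above 80%. The power figures rest on a correlation of about 0.5, which the plan does not state, and they describe the planning model, not the three-time-point analysis. The statement should be corrected because it is wrong as written and the correction is nearly free, not because the trial is materially underpowered.

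**What to change.** Keep the recruitment target of 48 and replace the dropout sentence in the Statistical Analysis Plan with, for example:

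> *48 patients allow for a dropout of up to 16.7% (8 patients). At 20% dropout about 38 remain, with power of about 79% for ankle ROM (secondary) and about 88% for MNSI (primary) under the planning assumptions (two measures, correlation 0.5).*

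Before adopting the power figures, the trial team should confirm the correlation from the original GPower run and recompute them if it was not 0.5. The first clause and the count of 38 stand regardless.

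The cost is one sentence. The stated allowance falls from 20% to 16.7%, which is slightly less favourable. No patients are added, the analysis is unchanged, and the recruitment figure in Participants and recruitment stays as it is.

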## **Methods/Design**

### **Study design and data collection**

This trial is designed as a single-blind, two-parallel arms RCT, wherein patients with DPN will be randomly allocated to either a control group (CG) or an intervention group (IG). This trial protocol follows all recommendations established by SPIRIT (2013) [47], has been approved by a research ethics committee (CAAE: 90331718.4.0000.0065), and was registered at ClinicalTrials.gov on July 2, 2019 (identifier NCT04008745).

Patients in the CG will not receive any specific intervention beyond the usual care, including treatment recommended by the medical team, pharmacological treatment, self-care guidelines, and a weekly telephone call to check on the adherence to care, which will be maintained in both groups [48]. Patients in the IG will perform a foot-related exercise program included in an educational booklet three times/week at home for 8 weeks. After 8 weeks, IG

participants will be encouraged to continue this exercise until the end of the study following the same schedule set in the intervention period. If proven effective, the benefits of the foot-related exercises protocol will be explained and offered to all control participants at the end of the study.

Patients from both groups will be evaluated for all outcomes at baseline (T0), 8 weeks (T8, end of intervention), and 16 weeks (T16, follow-up). All procedures in this study will follow the norms of the Operational Procedure Manual developed specifically for this research. The design and flowchart following the Consolidated Standards of Reporting Trials (CONSORT) guidelines [49] are presented in Fig. 1.

[figure not shown]

Figure 1 - Consolidated Standards of Reporting Trials (CONSORT) flow diagram illustrating the process of FOCA-II.

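### The plan tests at 5% in both the intention-to-treat and completers-only sets and does not say which decides efficacy or how a discordant pair is read

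*Combined protocol and SAP*

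**What the plan says.** Under Statistical Analysis Plan: "Inferential statistical analyses will be conducted using intention-to-treat and per protocol analyses". The second set is defined there: "The per-protocol analysis will include only those patients who complete follow-up in the allocated intervention group". No adherence threshold is attached. The model is common to both: "mixed general linear models of analysis of variance for repeated measures will be used to detect treatment–time interactions". So is the significance level, introduced by "Significant differences will be considered at" 5% with no analysis set named. For missing values, the method is to depend on the type of missingness, and in addition "imputation of the means for the missing data of variables with normal distribution will be conducted". Whether that is a group mean or a grand mean, and of the visit value or of the change, is not stated.

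Two other places bear on the point. Randomization, allocation, and blinding refers to a main treatment analysis, in the singular, without naming its analysis set. Study design and data collection makes a later offer of the exercises to control patients conditional on the words "If proven effective", without saying which analysis would show it.

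**The concern.** The aim is to show an effect of the exercise booklet over usual care, so this is a superiority question. The intention-to-treat comparison is protected by randomisation. The per-protocol comparison is not, because membership depends on completing follow-up, which happens after randomisation.

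With both sets tested at 5% and no ranking, a significant per-protocol result beside a null intention-to-treat result can be presented as success without breaching the plan. Two things are at stake: a second chance at significance, and the possibility that this second chance is biased. Patients know their allocation and only the exercise arm has 24 home sessions to do, so loss related to arm and response is plausible. The documents do not establish that it will happen.

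**Working it through.** **Inputs from the plan.** Alpha 0.05, power 0.80, effect sizes 0.26 and 0.23, two groups, two repeated measures, N of 32 and 40, 20% dropout, 48 recruited.

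**The plan's own figures.** For the within-between interaction F-test, noncentrality is f² × N × 2/(1 − ρ). With ρ = 0.5 (assumed; not stated):
- MNSI: 0.26² × 32 × 4 = 8.65, power 0.812.
- Ankle ROM: 0.23² × 40 × 4 = 8.46, power 0.809.

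Both sample sizes reproduce, and 40 × 1.2 = 48. The point does not rest on them. What matters here is that 20% loss leaves 48 × 0.8 = 38.4, about 38 completers.

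**Two chances, random loss.** If a random fraction p is retained, the full-set and completer statistics correlate at about √p, so √0.8 = 0.89. For two standard normal statistics, the chance under the null that at least one exceeds 1.96 in absolute value is:

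| Correlation | At least one significant |
|---|---|
| 0.80 | 7.8% |
| 0.85 | 7.5% |
| 0.89 | 7.1% |
| 0.90 | 7.0% |
| 0.95 | 6.5% |

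A null simulation of the T0-to-T8 change (24 per arm, loss near 20%, 40,000 runs) agrees: 6.9% to 7.2%.

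**Dependence on imputation.** Those figures treat intention-to-treat as having everyone's outcome. The patients who separate the two sets are the ones lost, whose values would be imputed. Null simulations with 24 per arm, 5 lost at random per arm and pre-post correlation 0.5 (assumed) give:

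| Single mean imputation | Intention-to-treat alone | Either set | Excess |
|---|---|---|---|
| Grand mean of T8 value | 4.7% | 7.0% | 2.3 points |
| Group mean of T8 value | 7.5% | 8.9% | 1.4 points |
| Grand mean of change | 5.1% | 5.1% | 0 |
| Group mean of change | 12.0% | 12.0% | 0 |

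In the last two rows, per-protocol was never significant on its own (0.0%). In the last row the faulty test is intention-to-treat itself.

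**Informative dropout (assumed).** Suppose 3 of 24 controls (12.5%) leave at random and 7 of 24 exercise patients (29.2%) leave, poor responders preferentially, with correlation 0.5 between response and leaving. The completer difference is then biased by 0.23 SD of change in favour of exercise, and the completers-only test rejects 11.3% of the time.
- Grand mean of T8 value: either set 13.3%, intention-to-treat alone 6.5%.
- Group mean of T8 value: 15.2% and 10.5%.
- Grand mean of change: 11.3% and 11.1%.
- Group mean of change: 22.2% for both.

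Set against an intention-to-treat analysis with every outcome observed (about 5%), the either-set rate is 9.3%, 13.5% and 25.7% at correlations of 0.3, 0.5 and 0.8. That comparator is optimistic when 20% are expected to drop out.

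**Extreme bound at 20% loss.** If the 20% lost from one arm were exactly its worst responders, the completer mean in that arm would shift by φ(0.842)/0.8 = 0.280/0.8 = 0.35 SD of change. With random loss the shift is 0.

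**The case against.** The strongest reply is that silence is not permission. A reader might infer that the plan gives the two sets equal standing, or that a per-protocol result beside a null intention-to-treat result supports the claim as written. The text says neither. It is equally open to a rule that both must be significant. With random loss and correlation 0.89, both would be significant by chance about 5% + 5% − 7.1% = 2.9% of the time, so there would be no inflation. The singular main treatment analysis suggests that a lead analysis was in mind, and the words "If proven effective" govern an offer to controls, not a statistical decision. All of this stands, and it limits the point to what the plan fails to rule out.

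A reader might also infer that exercise patients who dislike the programme drop out of the per-protocol set. Only leaving follow-up removes them; someone who stops exercising but attends assessments stays in. Both arms receive weekly calls, and unblinded controls may leave too. Differential loss is therefore an assumption.

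Finally, naming intention-to-treat might be taken to secure 5%. It does not if the gaps are filled by single mean imputation, as the tables show. This objection is right, and it changes the fix. It does not justify leaving the decisive set unnamed.

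**Conclusion.** The concern holds as a gap in the decision rule: two inferential analyses, one 5% level, no ranking and no rule for disagreement. It does not show that the plan authorises a per-protocol claim.

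If either set could support the claim, the error per test is about 6.5% to 7.8% with random loss. Of that, about 0 to 2 points is attributable to the second chance, depending on the imputation rule. Under the informative-dropout scenario the gain from making intention-to-treat decisive ranges from nothing (group mean of change) to about 7 points (13.3% to 6.5%, grand mean of T8 value). These larger figures rest on assumed loss by arm, an assumed link between response and leaving, and an assumed pre-post correlation, none of which the documents give. The 0.35 SD shift is an extreme bound, not an expectation. Having two primary outcomes is a separate multiplicity question and is not counted here.

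**What to change.** Add to the Statistical Analysis Plan that the intention-to-treat analysis (all randomised patients, as allocated) of the primary outcomes alone decides efficacy at 5%. State that the per-protocol result is a supportive estimate with a 95% confidence interval, and that it cannot overturn a null intention-to-treat result.

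In the same place, name one valid missing-data method for the intention-to-treat set in place of single mean imputation. Examples are a likelihood-based repeated-measures model using all observed visits, or multiple imputation, with a sensitivity analysis for data missing not at random. Without this, the first statement removes the second chance but does not hold the error at 5%, and intention-to-treat can carry over the completers' bias.

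The cost is a few sentences. The required sample of 40 before dropout is unaffected by naming the decisive set, and no new data are needed. The sponsor gives up the option of claiming efficacy on the per-protocol result.

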### **DPN symptoms**

Patients will answer the Brazilian version of the Michigan Neuropathy Screening Instrument (MNSI) [55]. This questionnaire has 15 questions about the sensitivity of the feet and legs and is self-administered. A score of 1 point is given for answers of “yes” for questions 1, 2, 3, 5, 6, 8, 9, 11, 12, 14, and 15 and “no” for questions 7 and 13. Questions 4 and 10 evaluate circulatory deficits and general asthenia, respectively, and neither are included in the final score. The sum of all scores ranges from 0 to 13, and the larger the score, the worse the DPN.

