### **Fuzzy classification of the DPN severity**

The classification of the DPN severity will be made using the Decision Support System for Classification of Diabetic Polyneuropathy [13,53] developed by the LaBIMPH and publicly available at: <http://www.usp.br/labimph/fuzzy/>. This decision will be based on fuzzy logic with the input variables of signs and symptoms extracted from the MNSI as well as tactile sensitivity (through the number of non-touch areas using a 10-g monofilament) and vibration sensitivity (by vibrating a tuning fork at 128 Hz), characterized as absent, present, or diminished. The software gives a score from 0 to 10, with higher scores indicating more severe DPN.

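### Filling missing values with an unspecified mean and analysing them as real data raises type I error to about 7–11% or shrinks the effect by up to 17–21% at the plan's own dropout rate

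*Combined protocol and SAP*

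**What the plan says.** All the missing-data text is in the Statistical Analysis Plan section of the combined protocol and SAP. It opens with a general rule: "The missing data will be treated by imputation methods depending on the type: missing completely at random, missing at random, or not at random". No method is attached to any of the three types. The only method named anywhere is for variables that pass a Kolmogorov–Smirnov normality check: "imputation of the means for the missing data of variables with normal distribution will be conducted". The next sentence moves to the analysis: "After that, mixed general linear models of analysis of variance for repeated measures will be used to detect" the treatment-by-time interaction over T0, T8 and T16, tested at 5%. The section mentions no multiple imputation, variance or degrees-of-freedom correction, or sensitivity analysis.

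The same section sets the expected amount of missing data: "Assuming a 20% dropout rate during the study, a sample size of 48 patients is needed".

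The primary outcomes are two bounded scores. For the MNSI, "The sum of all scores ranges from 0 to 13"; for DPN severity, "The software gives a score from 0 to 10". Higher is worse on both.

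**The concern.** The mean could be that of the patient's arm at that visit, of all patients at that visit, or of the patient's own other visits. The plan does not say which.

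- **Arm-by-visit mean.** The estimate is unchanged when data are missing completely at random. But the filled values add apparent sample size and no variation, so the standard error is too small.
- **Overall visit mean.** Each filled patient sits midway between the arms, which pulls the arms together.
- **Own mean.** A patient with only T0 is given zero change, which also pulls the arms together.

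The intention-to-treat result therefore depends on a choice the plan leaves open. One choice gives too many false positives and confidence intervals that are too narrow; the others give a diluted effect. The general rule does not settle it. The observed data cannot separate missing at random from missing not at random, and the plan does not say which it will assume. Normality, which triggers the mean rule, has nothing to do with why data are missing.

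Dropout linked to prognosis is plausible. Only the intervention group (IG) has to exercise three times a week, and patients know their allocation.

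**Working it through.** **Inputs from the documents.** 48 randomised, 40 evaluable, 20% dropout; visits T0, T8, T16; alpha 5%; effect sizes f = 0.26 (MNSI) and 0.23 (ankle ROM).

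**Assumptions.** 24 per arm (the allocation ratio is not stated); normal data with SD 1; equal correlation rho of 0.5 or 0.7 between visits; equal missingness per arm, completely at random except in step 4. Dropout timing is varied.

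**Plan's own figures.** For two groups and two measurements, lambda = N·f²·2/(1 − rho). With rho = 0.5 (assumed):
- MNSI: 32 × 0.26² × 2/0.5 = 8.65, power 0.812.
- ROM: 40 × 0.23² × 2/0.5 = 8.46, power 0.809.

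Both sample sizes reproduce. Then 40 × 1.2 = 48. The missing fraction is 8/48 = 16.7% (4 per arm). Taking 20% of 48 = 9.6, rounded up to 10, it is 10/48 = 20.8% (5 per arm).

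**1. Arm-mean filling, one visit, closed form.** With n observed per arm, the within-arm sum of squares is unchanged, but it is divided by 46 instead of 2n − 2, and the arm size is taken as 24 instead of n. The t statistic is inflated by √[(24/n) × 46/(2n − 2)].
- n = 20: √(1.200 × 1.211) = 1.205. The critical value 2.013 becomes 2.013/1.205 = 1.670 on 38 df, so the true type I error is 10.3%.
- n = 19: √(1.263 × 1.278) = 1.270. The threshold becomes 1.584 on 36 df, so the true error is 12.2%.

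**2. Arm-mean filling, planned three-visit test.** Type I error of the group-by-time F-test, 20,000 simulated trials per cell:

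| Missing per arm at T8 / T16 | rho 0.5 | rho 0.7 |
|---|---|---|
| 0 / 4 | 6.9% | 7.1% |
| 2 / 4 | 7.8% | 8.1% |
| 3 / 5 | 9.3% | 9.5% |
| 4 / 4 | 9.0% | 9.1% |
| 5 / 5 | 10.6% | 10.7% |

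Repeat runs with rho from 0.3 to 0.8 gave 6.6–11.1%. Overall-mean and own-mean filling gave 4.7–5.2%, and completers only 4.8–5.0%.

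**3. Dilution under the other two means.** Let the true effect be δ at both later visits.
- Overall mean, 4 per arm missing: IG mean (20δ + 4·δ/2)/24, minus control (CG) mean (4·δ/2)/24, is 20δ/24 = 0.833δ. With 5 missing it is 19δ/24 = 0.792δ. So 0.50 SD becomes 0.42 or 0.40 SD.
- Own mean, both visits missing: 4 of 24 get zero change, again 20δ/24.
- Own mean, only T16 missing: the fill averages T0 and T8 and carries δ/2, giving (20 + 4/2)/24 = 0.917δ.
- Staggered 2/4: T8 gives 22/24, so 0.46 SD. T16 gives 20/24 (overall), so 0.42 SD, or (20 + 2/2)/24 = 0.875 (own), so 0.44 SD.

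Simulation agrees. Power for a 0.50 SD effect with 4/4 missing, at rho 0.5 / 0.7: completers 0.34 / 0.54, overall mean 0.31 / 0.44, own mean 0.34 / 0.53.

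**4. Worst-case informative dropout, no true effect.** The 4 worst-baseline IG patients and 4 random CG patients leave before T8. The four largest of 24 standard normal values average about 1.43, so the remaining 20 IG patients have baseline mean −a, with a = 4 × 1.43/20 = 0.286. The bias in the IG-minus-CG change (negative means apparent benefit) is:

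| Analysis | Formula | rho 0.5 | rho 0.7 |
|---|---|---|---|
| Arm mean | −rho·a | −0.14 | −0.20 |
| Overall mean | −(20/24)·rho·a | −0.12 | −0.17 |
| Own mean | +(20/24)(1 − rho)·a | +0.12 | +0.07 |
| Completers only | +(1 − rho)·a | +0.14 | +0.09 |

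Simulated values for the three fills were −0.147/−0.198, −0.123/−0.164 and +0.117/+0.074.

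**The case against.** - **A completer analysis is planned.** The per-protocol analysis keeps only patients who finish follow-up, so a gap between the two results would show. This is partial protection: no precedence is stated, and completers are also biased in step 4.
- **The inflation needs one reading and the full dropout allowance.** This is correct. With only 2 per arm missing, arm-mean type I error is about 5.7–5.9% (T16 only) or 6.7–7.1% (both visits). But 20% is the plan's own planning figure.
- **Power holds at the planned effect.** In the sample-size design, f = 0.26 corresponds to a between-arm difference in change of 4 × 0.26 = 1.04 SD. With that effect at both visits, rho 0.5 and 4/4 missing, power is 0.87 (overall mean), 0.92 (own mean) and 0.93 (completers). With 5/5 missing, the overall mean still gives 0.83. The 0.50 SD used above is illustrative. This stands for power; the proportional shrinkage of the estimate is the same at any effect size.
- **The mechanism could be assumed rather than tested, and the cited reference may give methods.** This is fair, but the plan states neither the assumption nor the methods.
- **The statistician is blinded until the main analysis is done.** That makes steering the result harder. Arm means can still be filled using coded arms, and the choice of mean is still open.
- **The rule may not reach the primary outcomes.** This is correct: bounded scores may fail the normality check. The plan then names no specific method for them, so the primary analysis is under-specified either way.

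**Conclusion.** The concern holds. At the planned dropout rate every reading of the stated rule gives a wrong error rate or a diluted estimate:

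- arm-by-visit mean: type I error of about 7–11% for the three-visit test and 10–12% for a single visit;
- overall or own mean: error near 5%, but the effect shrinks by up to 17–21%.

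In the worst-case informative dropout, the spurious effect runs from an apparent benefit of about 0.2 SD to an apparent harm of about 0.12 SD, depending on the mean chosen.

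These figures rest on the assumptions listed above. That filled values are treated as observed is inferred from the order of steps and the absence of any correction; the plan does not say so in words. If dropout falls mainly in one arm, the dilution can be larger: all 10 missing in one arm under the overall mean gives 10/24 × 24/38 = 26%.

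**What to change.** Delete both the mean-imputation step and the choice of method by missingness type. Define the intention-to-treat analysis as a REML linear mixed model on all observed values, without imputation:

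- T0, T8 and T16 as responses and visit as a factor, with group-by-visit terms at T8 and T16 and equal T0 means in the two arms. Keeping T0 as a response retains patients who miss both later visits.
- Unstructured covariance, Kenward–Roger degrees of freedom, and a named simpler covariance if the model does not converge.
- The same model for both primary outcomes whatever the normality test shows, with a bootstrap interval as a check if residuals are clearly skewed.
- One sensitivity analysis for data missing not at random, such as multiple imputation with a delta shift in the IG.

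The essential part is a method valid under missing at random, plus that sensitivity analysis. Multiple imputation using T0 and all visits is an acceptable alternative main method.

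In 3,000 simulated trials the mixed model gave type I error of 4.8–5.7% (Monte Carlo SE 0.4 points) and estimates of −0.50 to −0.51 for a true −0.50 SD. Degrees of freedom were approximated as completers minus 2; Kenward–Roger was not coded. In the step 4 scenario its bias was −0.003 to +0.010 SD (1,000 trials). That is expected, because dropout there depends only on the observed baseline; no not-at-random case was simulated.

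The cost is SAP wording and standard software, with no extra patients or data. Intervals will be wider than arm-mean filling would show. The unstructured covariance needs six parameters from 48 patients, hence the fallback.
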